8.1.2 Serious Adverse Event (SAE)

A SAE is defined as, any untoward medical occurrence that at any dose:

- 1. Results in death.
- 2. Is life-threatening (defined as a participant at immediate risk of death at the time of the event). It does not include an event that, had it occurred in a more severe form, might have caused death.
- 3. Requires in-patient hospitalization or prolongation of existing hospitalization
- 4. Results in persistent or significant disability/ incapacity.
- 5. Is a congenital anomaly/ birth defect.
- 6. Consists of any other medically important condition.

8.1.3 Recording and Collection of Adverse Events

It is the responsibility of the investigator to collect all AEs (both serious and non-serious) derived from spontaneous, unsolicited reports of patients, by observation and by routine open questions.

AE reporting will extend from date of informed consent until completion of the final visit (EOT). Any ongoing AE at end of study visit should be followed until the outcome is evident and resolved, clinically stabilized or a plausible explanation has been found.

Pre-existing diseases (before participating in the study) are not considered to be AEs, unless the disease worsens during the study period. Concomitant diseases prior to enrolment will be recorded in the eCRF.

Signs and symptoms clearly associated with the disease under study (including symptoms of disease progression) should be reported as AEs if they are newly emergent (i.e., findings not previously observed in the patients), or are determined by the investigator as severe or a worsening, or if the investigator considers deterioration of disease-related signs and symptoms to be caused directly by the study drug.

Abnormal laboratory values/ ECGs/ vital signs/ ophthalmic/ physical and systemic examination should be reported as AEs *only* if the Investigator considers the abnormality as clinically relevant or significant or believes that the abnormality should be reported as an AE.

Any dose (and associated symptoms) given to the patient that exceeds the dose prescribed to the patient has, at a minimum, to be recorded as a non-serious AE in the patient file and CRF/ eCRF. Any case of overdose leading to an AE or SAE should be reported to Medical Monitor according to reporting requirements. In case of an accidental overdose, the patient should be monitored by the Investigator for any adverse clinical events, as deemed necessary by the Investigator.

After completion of all visit assessments, the Investigator must document any AEs arising from these assessments. In case of an SAE, the Investigator must also complete an SAE report form and report it to safety contact, as described in Section 8.1.4.2 Relationship to the Study Drug.

All AEs will be recorded in case report form (eCRF) regardless of the causal relationship to the study drug.

All AE records should contain AE term/ AE diagnosis, date of onset, severity, relationship to the study drug, outcome, date of recovery or outcome, action taken with the study drug, action taken with AE, AE leading to discontinuation of patient from study and whether the event is classified as serious.

The investigator must continue to follow-up the patient with all AEs regardless of the causal relationship to the study drug until the AE has resolved or until the condition stabilizes to an acceptable level or is determined to pose no issue, or until follow-up is no longer feasible.

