4.1.4 Patient Compliance

Compliance will be assessed by drug intake history. The number of capsules or amount of powder (and way it is subsequently administered, such as yoghurt, juice etc.) as well as the dose (strength) of study drug taken daily and weekly will be captured and this data will be later transcribed into the CRF.

Patients/caregivers judged to be non-compliant will be counselled on the importance of daily intake of study medication, as prescribed. A compliance between 80% - 125% will be desired for the adequate assessment of the study outcomes. Patients who are repeatedly non-compliant or have a compliance of less than outside 80-125% may be discontinued, at investigator's discretion after discussion with the medical monitor. Replacement of subjects will be at sponsor's discretion.

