6 ENDPOINTS AND VARIABLES

6.1 **Primary Variables**

The endpoints to assess efficacy (exploratory) will be adapted to the patient's age and the corresponding tests they are able to perform. When feasible the following will apply in accordance with standard clinical practice:

- Muscle strength measured using the modified Medical Research Council (MRC) scale to evaluate neck flexors, shoulder abductors, elbow flexors and extensors, wrist extensors, finger flexors, hip flexors, knee flexors and extensors, posterior foot flexors and plantar flexors.
- Clinical Global Impression (CGI) Scores given to caregivers and assessed by the investigators
- Number and frequency of adverse events (AEs), serious adverse events (SAEs) and AE leading to treatment discontinuation, throughout the study while on treatment with mexiletine
- Incidence of adverse events of special interest (AESI)
- Description over time of efficacy outcomes obtained from clinically indicated tests as per the treating physician typical clinical practice and according to patient's age and cohort.
- Any changes in frequency, treatment interruptions of mexiletine.

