8.1.1 Adverse Event

An AE is defined as any untoward medical occurrence in a patient or clinical investigation patient administered a pharmaceutical product and which does not necessarily have a causal relationship with this treatment. An AE can, therefore, be any unfavourable and unintended sign, symptom or disease (including intercurrent illness), deterioration of a pre-existing illness, accident, any suspected drug reaction, or a clinically relevant change of laboratory values temporally associated with the use of a medicinal (investigation) product, whether or not related to the medicinal (investigational) product and/ or study treatment.

A treatment emergent AE (TEAE) will be defined as an AE that begins or that worsens in severity after at least one dose of study drug has been administered.

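### Section 8.1.3 makes every dose above prescription an adverse event, so symptom-free excess doses enter the primary AE count beside clinical events

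*Protocol*

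**What the plan says.** Section 8.1.3 of the protocol rules that a dose given to a child which "exceeds the dose prescribed to the patient has, at a minimum, to be recorded as a non-serious AE in the patient file" (and in the CRF). The sentence opens with a parenthesis that brings associated symptoms into the record. It does not make symptoms a condition for recording. The next sentence reads: "Any case of overdose leading to an AE or SAE should be reported to Medical Monitor according to reporting requirements".

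Section 8.1.1 gives the general definition: "An AE is defined as any untoward medical occurrence in a patient or clinical investigation patient administered a pharmaceutical product". The same section makes any AE that starts or worsens after the first dose a treatment-emergent AE (TEAE).

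Section 6.1 lists among the primary variables: "Number and frequency of adverse events (AEs), serious adverse events (SAEs) and AE leading to treatment discontinuation, throughout the study while on treatment with mexiletine". Section 8.14 bases all AE summaries on TEAE records: an overall summary, then tables by preferred term and system organ class, relationship, maximum severity, seriousness and discontinuation. No category of TEAE is left out.

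Section 4.1.4 describes the intake data. The capsules or powder used, "as well as the dose (strength) of study drug taken daily and weekly will be captured". It also sets an adherence band: "A compliance between 80% - 125% will be desired for the adequate assessment of the study outcomes".

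**The concern.** A dose above prescription with no clinical consequence is a fact about exposure. Section 8.1.3 turns it into an adverse event, and the definition of a TEAE and section 8.14 then carry it into the primary AE number. A reader of the overall TEAE total could not tell how much of it is clinical.

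The records are also awkward to complete. Section 8.1.3 asks for relationship, outcome and recovery date for each AE, and these have no clear meaning when nothing happened to the child. The not-related category in section 8.1.4.2 requires a cause other than the study drug, which does not fit an excess of mexiletine itself. Such records could therefore end up in the treatment-related table.

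The setting makes some excess plausible: section 4.1.1 has capsules opened and the contents sprinkled or mixed when a child cannot swallow them. The registry plans for at least 10 evaluable children, so even a few non-clinical records can change the totals. Neither section 8.1.3 nor section 8.14 says whether the unit is a dose, a day or a run of days, so the number also depends on how a site enters them.

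**Working it through.** The protocol states no AE rate and no rate of excess intake, so there is no figure of its own to reproduce. The check is textual first and illustrative second.

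**Text, side by side**

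1. Section 8.1.1: an AE is an untoward medical occurrence.
2. Section 8.1.3, overdose rule: any dose above prescription is at least a non-serious AE. There is no tolerance and no symptom condition.
3. Section 8.1.3, next sentence: an overdose may lead to an AE. Cause and effect are separate here, so the overdose alone is not the AE.
4. Section 8.1.3, earlier paragraph: abnormal laboratory, ECG and vital-sign findings become AEs only if the investigator judges them clinically relevant or reportable. Excess doses have no such filter.
5. Sections 8.1.1, 6.1 and 8.14: an AE starting after the first dose is a TEAE, TEAEs are summarised without exclusions, and the AE number is a primary variable.

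Item 2 sits poorly with items 1 and 3. By item 5, its result reaches the primary AE count.

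**Illustration of size**

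Inputs from the protocol: at least 10 evaluable children (section 8.8); at least 104 weeks of follow-up (synopsis), that is 104 × 7 = 728 days.

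Assumptions not in the protocol: a share p of days with intake above prescription, from 0.1% to 10%; one AE record per such day; days independent.

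Expected records = 10 × 728 × p. Chance that a child has at least one = 1 − (1 − p)^728.

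| p | Expected records, 10 children | Chance of at least one per child |
|---|---|---|
| 0.1% | 7.28 | 0.517 |
| 0.5% | 36.4 | 0.974 |
| 1% | 72.8 | 0.999 |
| 5% | 364 | about 1 |
| 10% | 728 | about 1 |

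**Dependence on the counting unit**

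If a site rolled all excess days of a child into one record, the expected number would be 10 × the last column: 10 × 0.517 = 5.2 at p = 0.1%, and about 10 at p = 1% and above. At p = 10%, the same intake therefore yields about 10 or about 728 records, depending on entry practice.

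**After the change**

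With symptom-free excess counted separately, these records add 0 to the primary AE number, whatever p is.

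**The case against.** The case for leaving the text alone has several parts.

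- **Recording every excess is the cautious choice.** The children are very young, and dosing recommendations are still being established. Section 8.1.4.2 asks for all AEs, non-serious ones included, to be reported within 24 hours, and taking excess doses out of AE recording could lose that route. This stands, and the fix must keep the recording and the route.
- **The definition is broad.** Section 8.1.1 names accidents among possible AEs, and the overdose sentence may simply concern where clinical consequences are sent. This softens the conflict to loose wording, but symptom-free excess is still counted.
- **The records can be separated.** Tables by preferred term and a full listing with dates and frequency of occurrence would let a reader find them, and a continuing excess could be one record. Percentages, if per patient, would count a child once. This holds for the detailed tables. It does not hold for the overall TEAE summary or the primary AE number.

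Three stronger readings are tempting, and the protocol does not support them.

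- A reader might infer that the 80% to 125% band in section 4.1.4 contradicts the AE rule. A child whose overall intake is above 100% and within the band has indeed exceeded prescription at some time. But the band concerns adherence for assessing outcomes. It does not say that excess is acceptable for safety recording.
- A reader might infer that excess doses will swamp the AE count. No rate of excess is given, and AEs are collected at routine visits and from spontaneous reports, so a large volume is possible but not shown.
- A reader might infer a biased comparison of sprinkled with swallowed capsules. No formal comparison is planned. The analysis is descriptive, and excess linked to sprinkling would itself inform the suitability objective.

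**Conclusion.** The point holds in limited form. As written, section 8.1.3 puts symptom-free excess doses into a primary variable meant to describe clinical safety, and it does so against the sense of the AE definition and of its own next sentence. That follows from the text and needs no assumption.

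The size does need assumptions. About 7 to 728 records over 10 children corresponds to excess on 0.1% to 10% of days, independent days and one record per day. The true rate is unknown, and other entry practice would give far fewer records. The flaw is one of definition and presentation: it blurs the AE total in a very small registry, but it does not hide clinical events or invalidate the safety data. It is worth correcting because the correction is cheap.

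**What to change.** Reconcile sections 8.1.1 and 8.1.3, and carry the result into sections 6.1 and 8.14:

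- Keep recording every dose above prescription, with date, amount and cause, and keep its current safety reporting route, including the 24-hour reporting in section 8.1.4.2.
- In the primary AE variable and the overall TEAE summary, count as AEs only the associated signs, symptoms or clinically relevant findings.
- Show excess dosing on a separate line, split by with and without symptoms, and state the counting unit.
- Set no tolerance tied to the compliance band in section 4.1.4, so that no excess goes unrecorded.

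The cost is protocol wording and one extra table. The small downside is that the TEAE total no longer includes symptom-free excess doses, so the separate line must always be shown with it.

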8.1.4 Evaluation of Adverse Events

Each adverse event is evaluated depending on the following categories by the investigator.

8.1.4.1 Definition of severity of an AE

Wherever possible, all observed AEs will be graded using the CTCAE ver. 5.0. The severity of the AE shall be classified using the following grading.

- *Grade 1*: Mild; asymptomatic or mild symptoms, or clinical or diagnostic observations only, or intervention not indicated
- *Grade 2*: Moderate; minimal, local or non-invasive intervention indicated; limiting ageappropriate instrumental activities of daily living (preparing meals, shopping for groceries or clothes, using the telephone, managing money etc.).
- *Grade 3*: Severe or medically significant but not immediately life-threatening; hospitalization or prolongation of hospitalization indicated; disabling; limiting self-care (bathing, dressing and undressing, feeding self, using the toilet, taking medications and not bedridden).
- *Grade 4*: Life-threatening consequences; urgent intervention indicated.
- *Grade 5*: Death related to an AE.

8.1.4.2 Relationship to the Study Drug

The assessment of the relationship of an adverse event to the administration of study drug is based on the presence or absence of a "reasonable possibility" that investigational drug has caused the AE. An AE is considered to be "related" to the study medication if a causal relationship between the IMP and an AE is at least a reasonable possibility (i.e., the relationship cannot be ruled out). An AE related to the study drug is referred to as an adverse drug reaction (ADR).

The causal relationship between an adverse event and the study drug will be defined as below:

- *Not Related*: When the adverse event is definitely caused by the subject's clinical state, or the study procedure/ conditions or other concomitant drugs
- *Unlikely Related*: When the temporal association between the adverse event and the drug is such that the drug is not likely to have any reasonable association with the adverse event
- *Possibly Related*: When the adverse event follows a reasonable temporal sequence from the time of drug administration but could have been produced by the subject's clinical state or the study procedures/ conditions
- *Related*: When the adverse event follows a reasonable temporal sequence from the time of drug administration, abates upon discontinuation of the drug and reappears when the drug is reintroduced.

Reporting of Serious Adverse Events

All SAEs occurring after the time of informed consent until the final visit must be reported.

All AEs (non-serious) and SAEs should be reported by the investigator to the Medical Monitor and Safety Monitor via Email or telephone as soon as possible after the investigators become aware of its occurrence but no later than 24 hours regardless of the causal relationship with the study drug (following knowledge of the SAE). After receiving reports of the SAEs, the Safety Contact should communicate with the investigator to get additional information for evaluation

of SAEs. If the AE is fatal or life-threatening, the EU-QPPV/Lupin Safety Monitor must be notified immediately (as mentioned in the Safety Monitoring Plan), irrespective of the extent of information about the event available.

All AEs/SAEs shall be reported by investigator/ Sponsor/ sponsor designee as per applicable regulatory requirements.

Medical Monitor	Safety Monitor:	
[name], PhD	Clinical Safety, DSRM.	

8.1.4.3 Follow – Up of Serious Adverse Events (SAEs)

The investigator must continue to follow the patient until the SAE has resolved or until the condition stabilizes to an acceptable level or is determined to pose no issue, or until follow-up is no longer feasible. Any ongoing SAE at end of study visit should be followed until the outcome is evident and resolved, clinically stabilized or a plausible explanation has been found.

8.1.4.4 Suspected Unexpected Serious Adverse Reactions (SUSARs)

An SAE that is also an unexpected adverse drug reaction is called a Suspected Unexpected Serious Adverse Drug Reaction (SUSAR). Unexpected adverse reactions are adverse reactions, of which the nature, or severity, is not consistent with the applicable product information (e.g., IB for an unapproved investigational medicinal product or the Summary of Product Characteristics for an authorized medicinal product or available literature).

SUSARs will be reported in compliance with regulatory reporting requirements of participating countries by Lupin's pharmacovigilance group. The details of reporting of SAE, significant AEs and SUSARs will be captured in the Safety Management Plan (SMPs).

8.2 Adverse Events of Special Interest (AESI)

Adverse events, which are considered by the investigator to be a neurological disorder or gastrointestinal in nature, will be recorded as an adverse event of special interest.

All subjects should be carefully monitored for the diagnosis of listed AEs of special interest. All AEs of special interests should be evaluated properly and their relationship with the study drug should be recorded

Severe Cutaneous Adverse Reactions (SCARs)

Mexiletine is contraindicated in patients with known hypersensitivity to mexiletine, or to any of the excipients or to any local anaesthetic, as there is possibility of occurrence of potentially lethal severe cutaneous adverse reactions, usually severe cutaneous eruption along with fever, lymphadenopathy, hypereosinophilia, lymphocytosis or organ damage (notably liver and kidney).

Cardiac Arrhythmia

Mexiletine is a class I b antiarrhythmic drug according to the Vaughan Williams classification, and as such, it may induce an arrhythmia or accentuate a pre-existing arrhythmia, either diagnosed or undiagnosed. Mexiletine should be administered with caution in patients with pre-existing cardiac conduction anomalies. The advent (under mexiletine therapy) of an atrioventricular block, a permanent complete heart block, or a sinoatrial block necessitates the interruption of the mexiletine treatment.

Increased Frequency of Seizure Episodes in Patients with Epilepsy

Common elements of pathogenesis create a basis for the assumption that antiarrhythmic drugs may affect seizure phenomena and interact with antiepileptic drugs.

8.3 Physical and Systemic Examination

A physical examination will be performed at the time of screening to ensure patients comply with participation criteria. Other physical and or systemic examinations will be performed according to regular clinical practice or at the discretion of the treating physician.

8.4 Vital Signs

Vital signs, including blood pressure (BP), heart (pulse) rate (HR) will be measured according to regular clinical practice or at the discretion of the treating physician.

8.5 Electrocardiogram Assessments (ECGs)

A 12-lead ECG will be performed at screening and after screening according to regular clinical practice or at the discretion of the treating physician. Any abnormal findings will be evaluated for clinical significance.

8.6 Clinical Laboratory Examinations

Haematology tests, biochemistry, and urine analysis tests for safety assessment will be performed at screening and according to regular clinical practice or at the discretion of the treating physician.

Collection of Laboratory Samples

Sample collection and handling for laboratory tests will be performed according to regular clinical practice or at the discretion of the treating physician.

Any clinical test results outside the reference value range will be evaluated for clinical significance. After dosing, laboratory abnormalities considered by the investigator to have worsened compared to that prior to dosing will be recorded as AEs.

8.7 Pregnancy

Not applicable.

8.8 Sample Size

The number of patients, and type of study, was agreed with the paediatric committee (PDCO) during paediatric investigation plan (PIP) review. A total of at least 10 paediatric evaluable patients in cohorts 1 and 2. At least 4 patients from birth to less than 6 months (cohort 2) and at least 6 patients from 6 months to less than 6 years (cohort 1).

8.9 Statistical Methods

Summary descriptive statistics will be provided for all collected parameters. The categorical variables will be presented with frequency and percentages.

8.10 Handling of Missing Data

Missing data will be treated as missing, and no imputation will be done.

8.11 Patient Disposition

An overall summary of subject disposition will be presented using number and percentage (wherever applicable) for subjects screened, number enrolled, subjects who completed study

and subjects who discontinued, along with the reason of discontinuation. Disposition information will also be listed for each subject. Summary of screen failures will be presented. Number of subjects in each analysis population will be summarized.

8.12 Analysis Population

Safety Population: Safety population will comprise of the subjects who received at least one dose of mexiletine after the ICF was signed by their parents or legal guardians.

Intent to Treat (ITT) Population: ITT population will comprise of the subjects who have taken at least one dose of the study treatment and have at least one post-enrolment assessment done.

